3.2 Secondary Objectives (if applicable)

Assess the effects of solriamfetol on daytime sleepiness, fatigue, adherence with “sleep rescheduling”, and on daytime performance

4. Investigational Plan

All subjects will be monitored for 2 weeks prior to treatment, for 8 weeks during treatment, and for 2 weeks following treatment. Additionally, subjects will complete two questionnaires complete two questionnaires (Insomnia Severity Index [ISI] and Retrospective Sleep Continuity Assessment Questionnaire [RSCAQ]) 3 months after completing treatment.3 months after completing treatment. Subjects receiving solriamfetol will take medication at 2pm daily for 4 weeks. Medication use will also include a 1-week placebo run-in and a 3-week placebo “run-out” (8 weeks’ total). Note: This design was used for our prior trials of CBT-I with wake promoting medications. Subjects receiving CBT-I will have 8 weekly

sessions (up to 90 minutes in duration). Daily sleep diaries will be administered to assess for differences in sleep continuity between conditions and over time. Self-report weekly assessments will also be administered and will include standard retrospective measures of insomnia (ISI), sleepiness (Epworth Sleepiness Scale, ESS), depression (PHQ-9), fatigue (Functional Assessment of Chronic Illness Therapy – Fatigue Scale [*FACIT-Fatigue*]), PROMIS-Short Form 7a, and Brief Fatigue Inventory [BFI]), treatment acceptability (MITAS)), and daytime function (Functional Outcomes of Sleep-10 item, FOSQ-10). Daytime function will also be objectively assessed daily via Ecological Momentary Assessment and at the end of baseline treatment, and post treatment periods using a PVT phone-based app. Self-report assessments will be accomplished on-line via RedCap software and subjects will also be asked to complete weekly and monthly questionnaires via Hypknowledge (a PHT Penn Health Tech Clinical Research Tool) site.

Treatment Regimen (as noted above)

The first five participants will be enrolled slowly to observe whether any adverse responses occur (e.g., taking longer to fall asleep after medication administration at 2pm) that would necessitate protocol modifications, for instance to the timing of medication dosing, if not amount.

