5.2 Study Intervention Phase

See section 3.0 – Investigation Plan.

5.3 Phase II (if applicable include and add details about open label study phase if appropriate)

See section 3.0 – Investigation Plan.

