5.6 Study Endpoints

Primary hypothesis

1. Patients administered solriamfetol will have significantly greater improvements in sleep continuity (total wake time [TWT]) from baseline to post-treatment compared to patients administered placebos. Note: the study is powered for this hypothesis.

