5.6.1 Primary Study Endpoints

As noted in section 3.2

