5.6.2 Secondary Study Endpoints

1. Patients treated with CBT-I will have significantly greater improvements in sleep continuity from baseline to post-treatment compared to patients not administered CBT-I.
2. Patients treated with CBT-I in combination with solriamfetol will have significantly greater improvements in sleep continuity from baseline to post-treatment compared to patients treated with CBT-I alone.
3. **Exploratory hypotheses:** Patients treated with CBT-I in combination with solriamfetol will have significantly greater adherence with sleep restriction (i.e., sleep rescheduling, prescribed time to bed [PTTB]) and on daytime performance measures (e.g., ESS, FSS, etc.) compared to CBT-I alone.

i. Primary Safety Endpoints [if applicable]

As noted above, side effects will be assessed in several ways: daily assessments via the sleep diaries, weekly evaluation with a medical symptom checklist (52 symptoms where positive endorsements allow subjects to rate their average severity and number of days affected).

6. Study Population and Duration of Participation

Subjects 25 to 65 years old (inclusive) and who have a stable sleep/wake schedule (no shift work) with a preferred sleep phase between 10:00 PM and 8:00 AM. The recruitment sample will be populated by 40 completed subjects. The study duration will be 12 weeks, with a one-time follow-up at 3 months post-treatment.

a. Inclusion Criteria

Participants will meet the diagnostic criteria for Insomnia Disorder according to Diagnostic and Statistical Manual of Mental Disorders (DSM-5). The complaint of disturbed sleep will meet the following criteria:

- ≥ 30 minutes to fall asleep (SL) and/or ≥ 2 awakenings per night of ≥ 15 minutes duration and/or wake after sleep onset (WASO) time of ≥ 30 minutes where total sleep time (TST) did not exceed 6 hours (unless sleep efficiency [SE] is $\leq 80\%$).
- The problem is present for ≥ 3 nights per week.
- The problem duration exceeds ≥ 6 months.
- The complaint of impaired daytime function must include, although not limited to, the report of daytime fatigue, sleepiness, or both.

Additional inclusion criteria are as follows.

1. Aged 25 to 65 years (inclusive).
2. Have a preferred regular sleep phase between 10:00 PM and 8:00 AM.

b. Exclusion Criteria

Please note that all subjects will have to receive physician assent before being enrolled into the study.

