As noted above, side effects will be assessed in several ways: daily assessments via the sleep diaries and weekly evaluation with a medical symptom checklist (52 symptoms where positive endorsements allow subjects to rate their average severity and number of days affected).

10. Statistical Plan

k. Primary Endpoint

The primary endpoint is total wake time (time spent awake in bed) at the end of post-treatment, as measured via a web based self-report Sleep Diary.

I. Secondary Endpoints

1. Patients treated with CBT-I will have significantly greater improvements in sleep continuity from baseline to post-treatment compared to patients not administered CBT-I.
2. Patients treated with CBT-I in combination with solriamfetol will have significantly greater improvements in sleep continuity from baseline to post-treatment compared to patients treated with CBT-I alone.
3. Exploratory hypotheses: Patients treated with CBT-I in combination with solriamfetol will have significantly greater adherence with sleep restriction (i.e., sleep rescheduling, prescribed time to bed [PTTB]) and on daytime performance measures (e.g., ESS, FSS, etc.) compared to CBT-I alone.

m. Sample Size and Power Determination

To detect a clinically significant difference in self-reported total wake time of 30 minutes between the four treatment groups at the end of post-treatment using an ANOVA test, this study will require 10 subjects per group x 4 groups = 40 treatment completers. These calculations assume a standard deviation in total wake time of 19 minutes, with 80% power to detect the clinically significant change at an alpha level of .05. A total of 60 subjects will be recruited to obtain a sample of 40 subjects that complete the study due to attrition.

n. Statistical Methods

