Primary analyses will be conducted on an intention to treat basis and the trial conducted and reported according to CONSORT guidelines. Variable distributions will be examined to investigate homoscedasticity, outliers and normality, and corrected where appropriate using data transformations. The primary analysis is a 4(condition: +/- solriamfetol and +/- CBT-I) x 2(time: pre- and post-treatment) mixed ANOVA on absolute and percent change in total wake time ([TWT], time spent awake per night). If the interaction between condition and time is significant, Dunnett multiple comparisons will be conducted to further investigate differences in TWT between active treatment conditions versus the control condition to test Hypotheses 1-3. These analyses will be unadjusted in the first instance and then adjusted for covariates (primarily, age and sex).

An interim unadjusted analysis as per above will be conducted after 50% of the target sample have completed post-treatment (i.e., when N=20).

Secondary analyses include examining the interaction between treatment condition and time on other outcomes, including sleep continuity assessed via Sleep Diary (SL, WASO, EMA, TST, SE), insomnia (ISI), daytime sleepiness (ESS and KSS), fatigue (FSS and modified KSS), and daytime function (FOSQ-10, POMS, and PVT). Additionally, compliance to the medication (adherence to daily pill administration, as assessed via blister packs) and to sleep restriction (adherence to prescribed time to bed) will be investigated as covariates.

i. Baseline Data

Baseline and demographic characteristics will be summarized by standard descriptive statistics (including mean and standard deviation for continuous variables such as age and standard percentages for categorical variables such as gender).

ii. Pharmacokinetic Analysis **N/A**

iii. Interim Analysis **N/A**

iv. Safety Analysis

Side effects and adverse events will be assessed in several ways: daily assessments via the sleep diaries, and with a weekly evaluation using a medical symptoms checklist (52 symptoms where positive endorsements allow subjects to rate their average severity and number of days affected),

An adverse event will be defined as 1) any behavioral or health complaint spontaneously reported during the study, 2) an above threshold score on the study clinical assessment instruments (ESS, PHQ-9, or GAD-7), and/or a 20% increase in the medical symptom check list scores (frequency or severity).

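### Solriamfetol's effect on sleepiness, fatigue and daytime performance is a secondary objective, but no planned analysis isolates it

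*Combined protocol and SAP*

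**What the plan says.** **Objective.** Section 3.2, and objective 2 of the synopsis, read "Assess the effects of solriamfetol on daytime sleepiness, fatigue", and go on to adherence and daytime performance. Neither names a comparator or limits the objective to patients who receive CBT-I.

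**Hypothesis.** Section 5.6.2 item 3, repeated in Section 10 under Secondary Endpoints, labels adherence and the daytime measures exploratory. It names one comparison, combination treatment "on daytime performance measures (e.g., ESS, FSS, etc.) compared to CBT-I alone".

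**Analysis.** Section 10 (n) says: "Secondary analyses include examining the interaction between treatment condition and time on other outcomes". The outcomes it lists include "daytime sleepiness (ESS and KSS), fatigue (FSS and modified KSS), and daytime function (FOSQ-10, POMS, and PVT". The condition factor defined there has four levels, one per arm. Dunnett comparisons of each active arm with control follow a significant interaction, but they are described for TWT only.

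**Primary endpoint.** Section 5.6 states the primary hypothesis as "Patients administered solriamfetol will have significantly greater improvements in sleep continuity (total wake time [TWT]) from baseline to post-treatment", and Section 10 (k) says "The primary endpoint is total wake time (time spent awake in bed) at the end of post-treatment". Section 5.6.1, Primary Study Endpoints, reads only "As noted in section 3.2", and 3.2 is now the secondary objectives.

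**The concern.** The objective asks what solriamfetol does to sleepiness, fatigue and performance. Neither planned analysis answers that directly.

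- The four-level interaction asks whether the four arms change differently in any way. Section 14 (Risks) says CBT-I may temporarily increase fatigue and sleepiness, so CBT-I can produce a significant result when solriamfetol does nothing. No follow-up contrast is named for these outcomes to tell the two apart.
- The exploratory contrast does isolate solriamfetol, but only on top of CBT-I, and it uses 20 of the 40 completers. It leaves out solriamfetol without CBT-I, although the Background proposes stand-alone use for patients who do not tolerate sleep restriction.

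The rank is also unsettled: the same outcomes are secondary in 3.2 and 10 (n), and exploratory in 5.6.2 and its copy. If this stays open until results are known, both the label and the contrast can be chosen after the fact.

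**Working it through.** **1. The plan's own figure.** Section 10 (m) gives a 30-minute TWT difference, SD 19, alpha .05, 80% power, ANOVA, 10 per group. Take the least favourable arm means for a 30-minute range, (+15, 0, 0, −15). The noncentrality is n × Σ(mean − grand mean)² / SD² = 10 × 450 / 361 = 12.47. On 3 and 36 df this gives power 0.811, and 10 is the smallest n per group that reaches 0.80. The stated 40 completers reproduce, but they are sized for TWT and not for the outcomes discussed here.

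**2. Inputs for the secondary outcomes.** 10 completers per arm (Section 10 (m)) and alpha .05, taken as two-sided. The documents give no effect or SD for sleepiness, fatigue or performance, so an effect of d SD of the analysed change score is assumed and varied. With two time points, the condition by time interaction is the same test as a one-way ANOVA of change scores across the four arms.

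**3. Noncentrality of each test**, for an effect d that is the same with and without CBT-I, and no CBT-I effect:

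- Combination v CBT-I alone, 10 v 10: d² / (1/10 + 1/10) = 5d², on 1 and 18 df.
- Four-level interaction, arm means (d, d, 0, 0): 10 × 4 × (d/2)² = 10d², on 3 and 36 df.
- Solriamfetol v placebo over both CBT-I levels, 20 v 20: d² / (1/20 + 1/20) = 10d², on 1 and 36 df.

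The last two have the same noncentrality. The interaction loses power because it spreads it over 3 df.

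**4. Power**

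| Assumed d | 10 v 10 | Four-level interaction | 20 v 20 |
|---|---|---|---|
| 0.5 | 0.19 | 0.21 | 0.34 |
| 0.8 | 0.40 | 0.50 | 0.69 |
| 1.0 | 0.56 | 0.71 | 0.87 |
| 1.2 | 0.72 | 0.87 | 0.96 |
| d detectable at 80% power | 1.32 | 1.10 | 0.91 |

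Using the four-arm error (36 df) for the 10 v 10 contrast changes little: 0.41 at d = 0.8.

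**5. Interaction driven by CBT-I.** Let solriamfetol have no effect and CBT-I an effect of d. Two arms are again shifted by d, so the noncentrality is again 10d². The interaction is significant 50% of the time at 0.8 SD and 71% at 1.0 SD, and says nothing about solriamfetol.

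**6. Where pooling would not help.** If solriamfetol had a 0.8 SD effect with CBT-I and none without, the pooled effect would be (0.8 + 0)/2 = 0.4 SD. Its noncentrality would be 10 × 0.16 = 1.6, against 5 × 0.64 = 3.2 for 10 v 10. The gain in step 4 therefore rests on similar effects at both CBT-I levels.

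**The case against.** **The outcomes are in fact tested.** A reader might infer that the objective goes untested or unanswered. The documents do not support that: Section 10 (n) plans analyses of these outcomes in all four arms under the secondary label, in line with 3.2. What is missing is a contrast that isolates solriamfetol.

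**The primary endpoint is not in doubt.** Read literally, 5.6.1 would make these outcomes primary. That reading fails. Section 5.6, directly above it, names TWT and says the study is powered for it, and 10 (k) and the sample size text agree. Other pointers have drifted too: Section 5.2 says "See section 3.0 – Investigation Plan", but that plan is now Section 4. The pointer is a stale cross-reference to correct, not a third rank.

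**The half-sample contrast may be deliberate.** Adherence to a prescribed bedtime exists only in the CBT-I arms, and whether solriamfetol offsets sleepiness caused by CBT-I is a fair exploratory question. This stands, and the contrast should stay. It does not replace the wider contrast that 3.2 needs.

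**The power figures are illustrative.** True: 0.8 SD is an assumption, and the Publication Plan says the main intent is to obtain effect sizes. But the ordering of the 20 v 20 contrast over the other two holds across the whole assumed range when the effect is similar at both CBT-I levels. An effect-size aim also needs the estimate of interest to be named.

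**Not every named scale is scheduled.** Also true. FSS and KSS appear in 10 (n) but in neither Section 4 nor the Table of Instruments, which list BFI, FACIT-Fatigue and PROMIS for fatigue and ESS for sleepiness. A contrast can be added without new data only for scales that are collected.

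**Conclusion.** The point holds in this form: a stated secondary objective has no planned analysis that isolates the effect it asks about, and its outcomes carry two ranks. The full-sample test has no direction and can reflect CBT-I alone. The only directional contrast is exploratory, uses half the completers and leaves out stand-alone solriamfetol.

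At an assumed 0.8 SD, the planned analyses have 40% and 50% power, against 69% for the direct contrast. Effects detectable at 80% power are 1.32, 1.10 and 0.91 SD. These figures assume 10 completers per arm, two-sided .05, no CBT-I effect in the interaction figure, and a similar solriamfetol effect with and without CBT-I in the interaction and 20 v 20 figures. The TWT primary endpoint is untouched. The change should be made before results are seen.

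**What to change.** 1. In 5.6.2, 10 (l) and 10 (n), give sleepiness, fatigue and daytime performance one rank: secondary, as in 3.2.
2. Test each by one planned contrast, solriamfetol versus placebo across both CBT-I levels, with CBT-I as a factor in the model. Report the solriamfetol effect within each CBT-I level beside it.
3. Keep combination versus CBT-I alone as exploratory, and confine prescribed-bedtime adherence to the CBT-I arms.
4. Reconcile the FSS and KSS of 10 (n) with the scales in Section 4 and the Table of Instruments, and apply the contrast to those actually scheduled.
5. State whether the secondary p-values are adjusted for multiplicity; if not, label them unadjusted.
6. As a separate text correction, point 5.6.1 to the TWT endpoint of 5.6 and 10 (k).

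The cost is protocol and SAP wording and one contrast per outcome, with no extra patients and, for scheduled instruments, no new data. The drawback is that the pooled estimate averages over CBT-I and would dilute an effect present at one level only, which is why the within-level estimates must be shown with it.

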All study medication will be provided by Axsome Pharmaceuticals (no cost) and will be received, stored, and packaged by the University of Pennsylvania Investigational Drug Service (IDS). IDS will create blister packs for each patient that are identical and will allocate active medication and placebo according to treatment condition. This will enable double blinding of the study. All doses will be over-encapsulated, and all daily doses will be delivered as a single capsule. The use of blister

packs will also allow us to not only track adherence but to identify the patterning of medication use. Blister packs will be returned once a month when subjects will be evaluated and provided the next month's medication supply. The study CRC will dispense and receive the foil packs. The pattern of used and unused data will be coded.

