The study CRC will dispense and receive the foil packs. The pattern of used and unused medication will be captured by xeroxing or photographing each foil pack. Once a subject has completed their participation in the study (i.e., they have either completed the study, experienced treatment non-response or relapse, or withdrew from the study) they will be given the option to either (a) come to our office at [name] and return the blister packs to the CRC, who will bring them to IDS for destruction or (b) take the blister-packs to a local pharmacy and record a video of themselves placing the blister-packs in a safe drug disposal box, and share the video with study staff. This can be done via email or by uploading the video via REDCap (see example link: <https://redcap.med.upenn.edu/surveys/?s=XE4T3MKRTPNL7JY7>). The video will not include the subject's face or other identifying information. This will ensure that the medication is properly disposed of, and that this disposal is documented. Note: the study's informed consent already mentions that we cannot guarantee the security of email correspondence, and that email privacy is based on the email provider's user agreement. We will remind subjects of this so they can consider this factor when deciding whether to return the medication to our office (no video required) or to their local pharmacy's drug disposal box (video required).

h. Subject Compliance Monitoring

Pill use will be tracked per week via the sleep diary. These data will be compared to, and corroborated with, the foil pack data.

i. Return or Destruction of Investigational Product

Blister packs will be returned once the subject has completed the study. Following the archiving of the pill pack (pill utilization pattern captured by xeroxing or photograph) the study CRC will return the foil packs and remaining capsules to Investigational Drug Services of the University of Pennsylvania for destruction.

8. Study Procedures

All subjects will receive medication and complete daily sleep diaries and weekly questionnaires.

Does your study use MRI? (CAMRIS is the appropriate contact for all studies involving MRIs)

Yes No

Check of all that apply:

1.5T MRI
 3T MRI
 7TMRI

Does the MRI use investigational sequences and/or coils?

(See Experimental Device Clause)

Yes No Unsure

Does your study include pregnant women?

(See Pregnancy Clause and Justification)

Yes No

Does the MRI require the use of Contrast Agents?

(See Contrast Risks)

Yes No

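### Option (b) in section 7.g lets blister packs be discarded with no stated step to record which cells were used, and the pack-return provisions conflict on timing and route

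*Combined protocol and SAP*

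**What the plan says.** **Capture.** Section 7.g (Administration and Accountability) has the study coordinator (CRC) hand out and take back the packs, and states: "The pattern of used and unused medication will be captured by xeroxing or photographing each foil pack". Section 7.i has the CRC send packs and leftover capsules to the Investigational Drug Service after that archiving step.

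**Disposal.** The same section 7.g gives subjects who complete, do not respond, relapse or withdraw a choice. Under (a) they bring packs to the office. Under (b) they may "take the blister-packs to a local pharmacy and record a video of themselves placing the blister-packs in a safe drug disposal box", sharing the video by email or REDCap. The stated purpose is: "This will ensure that the medication is properly disposed of, and that this disposal is documented".

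**Timing of return.** Section 2 (Name and Description of the Investigational Product): "Blister packs will be returned once a month when subjects will be evaluated and provided the next month's medication supply". Section 7.i: "Blister packs will be returned once the subject has completed the study".

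**Use of the data.** Section 7.h tracks pill use through the sleep diary and adds: "These data will be compared to, and corroborated with, the foil pack data". Section 10.n, in its paragraph on secondary analyses, lists medication compliance as a covariate to be investigated, described as "adherence to daily pill administration, as assessed via blister packs".

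**The concern.** The pack is the only adherence source in the plan that does not depend on the subject's own report. Its value lies in the pattern of empty and full cells, and that pattern can be read only while someone has the pack. Option (b) sends the pack out of the study for good. What it requires in exchange is evidence that disposal took place, which need not show a single cell.

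At stake are the blister-pack covariate in the secondary analyses, the planned check of the diary against the packs, and the count of leftover capsules. For a subject who uses (b), any pack not already returned would leave only the diary entry that the pack was meant to verify. The conflicting return provisions make this worse, because the plan does not settle how many packs would still be in the subject's hands at the end.

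**Working it through.** The plan gives no figure on this point to reproduce: neither the uptake of option (b) nor the pack size is stated. The sample-size inputs in section 10.m (30 minutes, SD 19 minutes, 80% power, alpha .05, 10 × 4 = 40 completers) contain no adherence term. The check is therefore a comparison of the provisions, followed by simple counts.

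**Step 1. Follow a pack along each route.**

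- Route (a): subject → CRC → copy or photograph (7.g, 7.i) → Investigational Drug Service. The use pattern is recorded.
- Route (b): subject → pharmacy box, plus a video to staff. The CRC never holds the pack, so the sequence in 7.i cannot be carried out. No photograph, cell-level record or capsule count is specified in its place.

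**Step 2. Set the return provisions side by side.**

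| Section | When | How |
|---|---|---|
| 2 | Monthly, at evaluation and resupply | Returned |
| 7.g | End of participation, including withdrawal | Office, or pharmacy box with video |
| 7.i | Study completion | Returned, archived, then sent on by the CRC |
| 8.e Subject Withdrawal | Final visit after early withdrawal | Product collected |
| 8.e.i Withdrawn Subjects | After consent is withdrawn | Subject asked to return packs |

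There are two conflicting timings (section 2 against 7.i; 7.g agrees with 7.i) and a separate conflict of route (7.g option (b) against 7.i, 8.e and 8.e.i). Section 8.e.i also refers to a section 5g that does not exist. Sections 4 and 7.e repeat much of section 2's packaging text without the monthly sentence, so it is unclear whether that rule is in force.

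**Step 3. Locate adherence in the analysis.** Section 10.n makes the primary analysis intention to treat, unadjusted and then adjusted mainly for age and sex. Pill adherence appears only in the secondary-analysis paragraph. No primary or secondary hypothesis in section 5.6 uses it; the exploratory adherence hypothesis concerns prescribed time to bed.

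**Step 4. Size of the loss per subject on route (b), full course.**

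- Capsule days: 8 weeks × 7 = 56. Possible active days in the solriamfetol arms: 4 × 7 = 28.
- Calendar: 1 run-in week + 4 active + 3 run-out = 8, so active dosing falls in weeks 2 to 5.
- If nothing is returned before the end, the loss is up to 56 capsule days, including up to 28 active doses.
- If packs are returned monthly (assumption: four-week packs), only the pack for weeks 5 to 8 is outstanding. The loss is 4 × 7 = 28 capsule days, of which week 5 gives 7 active doses.
- In the two arms without solriamfetol, no active doses are involved.

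**Step 5. Number of subjects.** Uptake is assumed, since the documents give none.

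| Assumed uptake of (b) | Of 40 completers | On solriamfetol, if uptake is even across arms | Of 60 recruited |
|---|---|---|---|
| 10% | 4 | 2 | 6 |
| 25% | 10 | 5 | 15 |
| 50% | 20 | 10 | 30 |
| 75% | 30 | 15 | 45 |

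The third column halves the second, because two of the four equal arms receive solriamfetol.

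**The case against.** The strongest reply is that section 7.g states, without exception and before it offers the two routes, that each pack's use pattern will be copied or photographed. Read generously, that covers option (b), and only the mechanics are missing. This stands in part: the plan states an intention to record every pack, so a reader who infers that adherence is definitely not captured under (b) goes further than the text. But the sentence names no one to take the photograph and no time for it, and 7.i assumes that the CRC has the pack. Followed literally, (b) can be completed with nothing recorded.

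The second reply is that little depends on the measure. That also stands. It is a covariate in secondary analyses, and diary pill use remains as another source. What is lost is the independent check on that diary.

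Third, withdrawn subjects are partly covered by the final collection visit in 8.e and the return request in 8.e.i. These help, but they conflict with 7.g, which offers (b) to the same people.

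Fourth, monthly return would protect earlier packs. It would, if it is in force, but the last pack would still be exposed. Nor can one say that the plan has no monthly contact at all: section 4 mentions monthly online questionnaires, although the instrument table in section 8.g has no monthly column.

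**Conclusion.** The gap is real and should be closed, but its reach is limited. Under option (b), blister-pack adherence and its check against the diary may be lost for any pack not already returned: 28 to 56 capsule days per full-course subject, on the assumption of four-week packs. The number of subjects is unknown. Remote consent, remote therapy and a catchment of up to 60 miles make use of (b) plausible, but the table above rests on assumed rates.

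Three stronger readings are tempting and not supported:

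- That the trial's main result is affected. The primary analysis, sample size and power do not use pill adherence.
- That the protocol-compliant population will mix two kinds of adherence measurement. Section 10.o lists that population without defining it, and nothing ties membership to packs.
- That poor adherers will choose (b). This is possible, and it would make the missing data informative, but the documents offer no evidence either way.

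**What to change.** 1. In 7.g, make option (b) conditional on the subject first sharing a legible photograph of every blister card, marked with a non-identifying subject code, through REDCap or the same route as the video. State that this comes before disposal and applies to withdrawn subjects as well.
2. Reconcile sections 2, 7.g, 7.i, 8.e and 8.e.i into one statement of when packs are returned, by which routes, who records the use pattern and at what point. Correct the reference to section 5g at the same time.

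The photograph supplies the record that 7.g already promises. Like a copy made by the CRC, it shows emptied cells rather than capsules swallowed, so the diary comparison in 7.h is still needed.

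Cost: one upload field next to the one that already takes the video, edits to five short passages of text, and about a minute of subject time per card (an estimate). No analysis, sample size or treatment rule changes.
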